Multiple methods of ex-vivo and in-vivo T-cell depletion have been reported in the HLA-haploidentical HSCT setting.^{22,23} CD34+ stem cells can be positively selected and administered as a graft product, or negative selection can be performed to remove specific components such as T cells from the graft product. CD34+ positive selection, or combined CD3+ and CD19+ negative selection, results in the loss of cells that are important for preventing infections and relapse.^{9,10,24-26} In order to reduce the risk of infections and relapse, several centers have more recently implemented a TCR $\alpha\beta$ + T-cell/CD19+ B-cell depletion approach.¹¹ Selective TCR $\alpha\beta$ +/CD19+ depletion aims to remove TCR $\alpha\beta$ + T-cells from the graft which have alloreactive potential and can cause GVHD, as well as antigen-presenting B cells which also contribute to GVHD.²⁷⁻³⁰ However, TCR $\gamma\delta$ + T-cells purposefully remain in the graft to facilitate engraftment, reduce the risk of infections, and reduce the risk of leukemia relapse without causing GVHD as TCR $\gamma\delta$ + T-cells do not have alloreactive capacity.^{18,31-34} Donor NK cells also remain in the graft and offer activity during the early weeks following HSCT until mature donor graft-derived NK cell reconstitution occurs.^{16,35} The large number of stem cells typically infused with this type of product can also allow early robust neutrophil engraftment which may decrease early bacterial infections.

Promising clinical results have been recently reported in children and young adults treated with TCR $\alpha\beta$ +/CD19+ depleted HSCT (Table 1). Bertaina et al evaluated 23 children with non-malignant hematological disorders who underwent haploidentical transplantation using TCR $\alpha\beta$ +/CD19+ depletion.³⁶ No acute GVHD prophylaxis was administered. All but 4 of the patients engrafted. Three patients developed grade I-II acute GVHD of the skin, and there was no occurrence of visceral acute or chronic GVHD. The 2-year probability of disease-free survival was 91.1%. Other pediatric experiences have been published since, and are also summarized in Table 1.^{19-21,36,37} All patients received less than 2×10^5 TCR $\alpha\beta$ + T cells per kg and the median CD34+ cell doses were 9×10^6 /kg or greater. Rates of Grades 3-4 acute GVHD were low. Several studies did not use additional GVHD prophylaxis. Overall survival at various timepoints ranged from 50-97%.

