Table 1. PREVIOUS WORK DONE IN THE AREA

Study	Bertania et al³⁶	Balashov³⁷	Lang¹⁹	Maschan²⁰	Locatelli²¹
Year	2014	2015	2015	2016	2017
PMID	24869942	26187864	26039210	26808573	28588018
No of pts	23	37	41	33	80
Adult /pediatric	Pediatric	Pediatric	Pediatric	Pediatric	Pediatric
Disease Indication	Non-malignant disorders	Primary Immune Deficiencies	ALL (20) AML(9) MDS/JMML (3) Solid tumors (4) Nonmalignant (5)	AML	ALL, AML
Donor	Haplo	MUD (n=27) Haplo (n=10)	≥2 HLA loci-mismatched parents	MUD MMRD Haplo	Haplo
GvHD prophylaxis	None	Tac/MTX (n=34) Tac/MMF (N=2) CSA/MTX (n=1)	MMF until day +30	None	None
CD34+ Dose	15.8x10 ⁶ /kg (10.2-40.0)	11.7x10 ⁶ /kg (5.9-21.3)	14.9x10 ⁶ /kg	9x10 ⁶ /kg (3.8-21)	13.9x10 ⁶ /kg (6-40.44)
Alpha/beta Dose	4x10 ⁴ /kg (1-9.5)	10.6x10 ³ /kg (0.8-368)	16.9x10 ³ /kg	20x10 ³ /kg (2.9-126)	0.047x10 ⁶ /kg (0.002-0.099)
Gamma/delta Dose	9.4x10 ⁶ /kg (1.6-95.4)		11.0x10 ⁶ /kg	9x10 ⁶ /kg (1-30)	8.1x10 ⁶ /kg (0.86-56.7)
Neutrophil Engraftment	Day+13 (10-20)	Day +16 (11-28)	Day +10 (7-21)	Day +16	Day +13 (9-19)
GVHD	Grade 1-2: 3 pts No chronic	Grade 2: 7 pts Grade 4: 1 pt Chronic: 1 pt	Grade 2: 4 pts Grade 3-4: 6 pts Chronic: 9 pts	Grade 2-3:14 pts Chronic: 10 pts	Grade 1-2: 24 pts Chronic: 4 pts
Graft Failure	2 Primary 2 Secondary	2 Primary 8 Secondary	5		2
Malignancy Relapse			17 pts	10 pts	19 pts
Infection	Viral reactivations: 9	CMV: 16pts, 5 with disease	Not Reported	CMV Reactivation: 52% EBV Reactivation: 50%	Not reported
Survival	2yr OS 91% 2yr DFS 91%	2yr OS 97% 2yr EFS 68%	If in CR1-3: 100% If in active disease: 0%	2yr OS 68% 2yr EFS 60%	OS 72% 5 years

RATIONALE

Based on these results we propose the use of $\alpha\beta$ T-cell/CD19+ B-cell depleted stem cells in mismatched related and unrelated donor HSCT for malignant and nonmalignant disorders in pediatric and adolescent/young adult patients. Mismatched related donors provide an allogeneic HSCT option for essentially all patients in need of HSCT. This approach reduces the risk of acute GVHD and reduces the need for GVHD prophylaxis, either of which is poorly tolerated by certain patient groups. Additionally, transplantation can be performed without delay which can be critical in patients with high risk malignant disease or very severe non-malignant disorders requiring urgent treatment.

IV. RESEARCH PLAN

1a. How many subjects will be studied?

We will enroll up to 80 patients.

1b. How will subjects be selected for this study?

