higher will be recorded on case report forms. Because the primary aim of this study is to assess safety of the infusion of TCR $\alpha\beta$ +/CD19+ depleted HSCT, and infusion reactions or other adverse events are expected to occur within 48 hours of the initial product infusion, we will only monitor and record AEs for the first week of the study. Any “attributable” events noted after this first week will be recorded and reported according to applicable institutional and federal regulations. Patients will be followed through Day +100 for endpoints including engraftment, acute GVHD, and event-free survival.

Expected events are those that have been previously identified as resulting from administration of the protocol therapy, those that can be attributed to the underlying condition, and/or those associated with transplant. An adverse event is considered unexpected, for reporting purposes only, when either the type of event or the severity of the event is not listed in the protocol and/or investigational brochure.

Please note that for the purpose of this study we will exclude the report of hematologic toxicities, as these subjects, by virtue of their underlying disease and/or condition and the transplant regimen, will develop hematologic abnormalities that otherwise would qualify as toxicity. Hematologic toxicities which are attributable to the underlying hematological disease and/or HCT preparative regimen will not be considered adverse events. In the event that any of these known complications of transplant or hematologic toxicities are thought to be at least possibly attributable to the study, the event will be recorded and subsequently reported to the IRB and FDA according to current reporting requirements.

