cramps, abdominal pain, throat pain etc), cholecystitis, allergic reaction, serum sickness, enterocolitis, infections, viral reactivations, upper respiratory infection, urinary tract infection, leukocytopenia, lymphocytopenia, neutropenia, thrombocytopenia, bleeding complications such as epistaxis, hematemesis, petechiae, subconjunctival hemorrhage, weight gain/loss, fluid retention, acidosis, alkalosis, anorexia, dehydration, glucose intolerance, electrolyte disturbances, iron overload, generalized muscle weakness, reversible posterior leukoencephalopathy syndrome, bladder spasm, cystitis, noninfective, hematuria, urinary frequency, urinary urgency, irregular menstruation, pruritis, hypertension, depression, anxiety, purpura, and petechiae. It is notable that adverse events following allogeneic hematopoietic cell transplantation can be severe and life-threatening. Acute graft versus host disease, infections, mixed chimerism, cytopenias, and graft failure are all known complications of allogeneic HCT, and can result in death. Organ failure may also occur due to toxicities of chemotherapy, infections, thrombotic microangiopathy, or other reasons. For the purposes of this study, the listed events that are </= grade 3 will not be considered adverse events. All listed events that are grade 4 or 5 will be recorded on the AE case report forms (CRF) and reported according to current IRB guidelines. In the event that any of these known complications are thought to be at least possibly attributable to the study procedure, and not to the allogeneic hematopoietic cell transplantation and expected complications, the event will be recorded and subsequently reported to the IRB and FDA according to current reporting requirements. Acute GVHD, mixed chimerism, and graft failure are not considered AEs during the study (they are captured as endpoints).

Medical conditions/diseases present before the infusion of TCR $\alpha\beta$ +/CD19+ depleted HSCT are only considered adverse events if they worsen after the infusion of TCR $\alpha\beta$ +/CD19+ depleted HSCT. Abnormal laboratory values or test results constitute adverse events only if they induce clinical signs or symptoms, are considered clinically significant, or require therapy.

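### Infection is not an endpoint and adverse events are recorded for one week at grade 4 or higher, so non-fatal infection after week 1 is not systematically captured

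*Combined protocol and SAP*

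**What the plan says.** **Collection window.** Section X.8 states that "we will only monitor and record AEs for the first week of the study". The reason given is that "infusion reactions or other adverse events are expected to occur within 48 hours of the initial product infusion".

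**Severity threshold.** Only events of grade 4 or higher go on the case report forms. Section X.8 lists infections and viral reactivations among the known complications of transplant, and listed events at or below "grade 3 will not be considered adverse events".

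**Exception after week 1.** Attributable "events noted after this first week will be recorded and reported according to applicable institutional and federal regulations". For a listed complication, attribution means at least possibly due to the study procedure "and not to the allogeneic hematopoietic cell transplantation and expected complications".

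**A second statement on grade 4 and 5.** Section X.8 also says that every listed event of grade 4 or 5 is recorded on the AE case report forms. It does not repeat the one-week limit.

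**Substitute endpoints.** Section X.8 says "Acute GVHD, mixed chimerism, and graft failure are not considered AEs during the study (they are captured as endpoints"). Infections are named beside these complications as a possible cause of death, but Section V has no infection endpoint and Section VII.2 no infection analysis.

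**Role of infection in the argument.** Section III says that TCR gamma-delta T cells "remain in the graft to facilitate engraftment, reduce the risk of infections, and reduce the risk of leukemia relapse without causing GVHD". Section II argues similarly against CD34+ selection. Table 1 has an infection row, which for one series reads "CMV Reactivation: 52% EBV Reactivation: 50" percent.

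**The concern.** The one-week window suits infusion reactions, which are the primary endpoint. The purpose in Section I is wider, covering safety and efficacy of the transplant, and the hypothesis is that the products are safe. Infection is an expected hazard of a T-cell-depleted graft, and one that the protocol says this method should lessen.

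GVHD, mixed chimerism and graft failure leave AE reporting because endpoints pick them up. Infection is largely removed from AE reporting by the window and the grade threshold, and no endpoint picks it up. Followed as written, the trial could report the product as safe with little to say about non-fatal CMV disease, sepsis or viral reactivation after week 1.

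**Working it through.** The plan gives no figure for infection to reproduce. The check sets the provisions side by side and then sizes what is missed.

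**1. Where each outcome is captured in the readable text**

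| Outcome | Captured? |
|---|---|
| Fatal infection to Day +100 | Yes: death is an EFS event (Section V), counts toward the stopping rule if classed as TRM (VII.3), and protocol-associated deaths go to the monitor (VIII.1) |
| Grade 4 non-fatal infection after week 1 | Unclear: no under the one-week sentence, yes under the grade 4 or 5 sentence |
| Infection of grade 3 or lower, any time | No, unless attributed to the study procedure and not to the transplant |
| Cell product given to control infection | The product is recorded, but Section V excludes it as an EFS event |
| Acute GVHD, mixed chimerism, graft failure | Yes, as endpoints |

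**2. Share of the follow-up covered.** The window is 7 of 100 days, or 7%. It closes before the typical neutrophil engraftment days in Table 1 (Day +10 to +16). As an illustration, assume a constant infection hazard to Day 100 and no competing deaths. With Day-100 incidence c, h = −ln(1 − c)/100, and the share of first infections falling in week 1 is (1 − e^(−7h))/c:
- c = 25%: 0.0199/0.25 = 8.0%
- c = 40%: 0.0351/0.40 = 8.8%
- c = 50%: 0.0474/0.50 = 9.5%

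The grade-4 threshold would remove further events even inside week 1.

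**3. How common infection was in earlier series (Table 1)**
- Non-malignant disorders, n = 23: 9 viral reactivations, against 3 patients with acute GVHD and 2 + 2 = 4 graft failures.
- Primary immune deficiency, n = 37: CMV in 16 (16/37 = 43%), with disease in 5 (5/37 = 14%), against 7 + 1 = 8 with acute GVHD of grade 2 or 4 and 2 + 8 = 10 graft failures.
- AML, n = 33: CMV reactivation 52% (0.52 × 33 ≈ 17 patients) and EBV 50%, against 14 with grade 2-3 acute GVHD.
- The other two series did not report infection.

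Where reported, viral events were at least as frequent as the complications this trial does make endpoints.

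**4. Mortality coverage.** An exact binomial recursion over the Appendix 2 boundaries, checked after every patient from 10 to 73 and stopping at or above the listed number, gives P(stop | TRM 30%) = 0.988. The rule therefore reacts to high TRM, including fatal infection if classed as TRM. The same calculation gives P(never stop) = 0.012 at 30% and 0.623 at 15%. These do not match the stated type I error of 0.05 and power above 80%, but that is a separate issue and nothing here depends on it.

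**5. What an added endpoint would give.** If every patient's status to Day +100 is known, cumulative incidence with death competing equals the simple proportion. Exact (Clopper-Pearson) 95% intervals for 80 patients at assumed rates are:
- 10% (8/80): 4.4% to 18.8%
- 25% (20/80): 16.0% to 35.9%
- 40% (32/80): 29.2% to 51.6%
- 50% (40/80): 38.6% to 61.4%

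**The case against.** **Safety after week 1 is not ignored.** A reader might infer that the trial cannot show whether the graft is safe at all. The documents do not support that. TRM to Day 100 drives a stopping rule, death is an EFS event, survival is collected at 1 year, and the monitor reviews deaths. The primary objective is limited to infusion safety. This stands, and it narrows the gap to non-fatal infection.

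**Severe infections may be recorded anyway.** The grade 4 or 5 sentence has no time limit, and the serious-event provisions in Sections X.7 and X.8 state none either. This partly stands: the text is contradictory on grade 4 rather than plainly silent. It does not reach infections of grade 3 or lower, and expedited reporting is not a planned summary of incidence.

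**Attributable events are recorded later.** True, but weak protection. Infections are already listed as expected, and in a single-arm trial where the study graft is the transplant, there is little basis for attributing an infection to one and not the other.

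**Infection is not the main rationale.** A reader might infer that lower infection risk is why the trial exists. The Rationale in Section III rests on donor access, less GVHD and prophylaxis, and avoiding delay. Infection is a supporting argument in Sections II and III. This stands.

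**Monitoring may be in redacted text.** Required Observations, Post-HSCT and Supportive therapy are blacked out, so clinical surveillance may be described there. It therefore cannot be said that Day +100 infection data exist and are being discarded. The readable endpoint and analysis sections still contain no infection outcome.

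**Conclusion.** The concern holds in a limited form. Routine AE recording covers 7 of 100 days at grade 4 or higher, and infection has no endpoint. Non-fatal infectious morbidity after week 1, and infection of grade 3 or lower at any time, is therefore not systematically captured. Separately, the one-week limit and the untimed grade 4 or 5 sentence in Section X.8 conflict and must be reconciled. The primary infusion endpoint is unaffected.

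Two further inferences go too far:
- Scaling the Table 1 rates to 80 patients suggests about 35 to 42 CMV reactivations (0.432 × 80 = 34.6; 0.52 × 80 = 41.6) and about 11 cases of CMV disease (0.135 × 80 = 10.8). These are not expected counts. They come from primary immune deficiency and AML series with different donors and prophylaxis, and this trial's immune suppression section is redacted.
- An added endpoint would not test an advantage over CD34+ selection, because there is no comparator and no stated reference rate. It would only describe infection, to within about 11 points at an assumed 40%.

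The conclusion rests on the readable text. The constant-hazard figures and infection rates in the working are assumptions.

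**What to change.** 1. Keep the one-week window in Section X.8 for infusion reactions, and say whether it runs from enrollment or infusion.
2. Add to Section V a descriptive secondary safety endpoint: Day +100 cumulative incidence, with death as a competing event, of (a) treated viral reactivation or disease and (b) other infection of grade 3 or higher. The method is already planned in Section VII.2 for engraftment and acute GVHD.
3. State in Section X.8 that these infections are exempt from the grade-4 threshold, and that they and all deaths with cause are recorded through Day +100. Cause of death would also support TRM classification, since TRM is not defined in the readable text.
4. Reconcile the one-week limit with the grade 4 or 5 sentence.
5. Base the endpoint on clinically detected events abstracted from clinical records, because any surveillance schedule lies in redacted text. Say how patients who leave the study before Day +100 under Section VI are handled.

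**Cost:** protocol wording and modest data entry, roughly one extra case report form page per patient within the existing Day +100 follow-up. Abstracting clinically detected events should need no new visits or tests.

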- [REDACTED]
- [REDACTED]

Required Observations:

[REDACTED]

Day of Graft Infusion: [REDACTED]

[REDACTED]

Post-HSCT: [REDACTED]

[REDACTED]

V. EVALUATION CRITERIA

Primary Endpoint:

The primary endpoint of the study is safety of infusion of TCR $\alpha\beta$ +/CD19+ depleted donor grafts.

We will determine the frequency and characteristics of potential infusion-related toxicity. Experience at our center using CD34+ selected stem cells has shown infusion related toxicity occurs at an incidence of <5%. We previously observed zero infusion reactions in 22 patients who received a CD34+ selected boost product as part of a CCHMC study (IRB# 2010-2344), and 2 infusion reactions among 55 infusions which were performed as part of clinical care including 1 occurrence of hypertension, and 1 occurrence of urticaria that resolved with anti-histamine administration. While there is little expectation of infusion-related toxicity, the incidence of infusion-related reactions will be recorded and evaluated.

Secondary Endpoints:

The secondary endpoints of the study are to assess engraftment and acute GVHD incidence.

Engraftment:

Engraftment and graft function are monitored on a clinical basis. Neutrophil recovery will be defined as the first of 3 consecutive days that the absolute neutrophil count is 500 cells/mcL. Platelet recovery will be defined as the first of 3 consecutive days that the platelet count is greater than 20 without any platelet cell transfusions in the previous 7 days. Initial donor-derived hematopoietic cell recovery will be defined as having 95% or greater donor-derived cells. Initial mixed donor and recipient-derived engraftment will be defined as having less

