An adverse event is any new, undesirable medical occurrence or change of an existing condition in a subject that occurs during treatment (which may include a specified post treatment period), whether or not considered to be product related. Abnormal laboratory findings considered by the investigator to be clinically significant, e.g. those that are unusual or unusually severe for the population being studied, should be recorded as adverse events.

Serious Adverse Event

A serious adverse event is defined by regulatory/clinical criteria. It is one that suggests a significant hazard or side effect, regardless of the investigator's or sponsor's opinion on the relationship to study material. This includes, but may not be limited to, any event that (at any dose):

- is fatal;
- is life threatening (places the subject at immediate risk of death);
- requires intensive care;
- is persistent and results in significant disability/incapacity;
- Hospitalization
- Disability or Permanent Damage
- Congenital Anomaly/Birth Defect
- Require Intervention to Prevent Permanent Impairment or Damage (this one may only apply to investigational devices)
- Other Serious (Important Medical Events)
- For an event that may not be immediately life threatening or result in death or hospitalization, but may jeopardize the patient or require intervention to prevent one of the outcomes listed above, or result in urgent investigation, may be considered serious.

Important medical events that may not be immediately life threatening or result in death or hospitalization, but may jeopardize the patient or require intervention to prevent one of the outcomes listed above, or result in urgent investigation, may be considered serious.

8. Adverse Event Reporting:

Safety and tolerability will be assessed according to the Common Terminology Criteria for Adverse Events v5.0 (CTCAE published November 27, 2017). The principal investigator(s) or designee will review adverse events closely and assess the event's relationship to study procedures to determine whether the event is unrelated or, unlikely, possibly, probably or definitely related to the study procedures, especially in context of the underlying disease and baseline lab values for the patient.

Allogeneic HSCT is known to be a high-risk procedure with many complications and a gross mortality risk of approximately 70%. Only adverse events of grade 4 or
Protocol v01.27.2021
IRB# 2018-8568

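### Section X.8's grade 4+ and listed-event filters are not reconciled with the ungraded primary endpoint in Section V, so non-serious infusion reactions of grade 3 or lower can be under-recorded

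*Combined protocol and SAP*

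**What the plan says.** **Section V, Primary Endpoint.** The endpoint is safety of infusion. The protocol states: "We will determine the frequency and characteristics of potential infusion-related toxicity", and that "the incidence of infusion-related reactions will be recorded and evaluated". No grade limit is given. The comparison is the centre's experience with CD34+ selected cells, put at under 5%. Its basis is "We previously observed zero infusion reactions in 22 patients who received a CD34+ selected boost product", plus two reactions among 55 clinical infusions: "1 occurrence of hypertension, and 1 occurrence of urticaria that resolved with anti-histamine administration". Neither reaction is graded.

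**Section X.8, Adverse Event Reporting.** One sentence, broken across a page, reads "Only adverse events of grade 4 or" and then "higher will be recorded on case report forms". X.8 next limits adverse event recording to the first week. It gives as reasons that infusion safety is the primary aim and that "infusion reactions or other adverse events are expected to occur within 48 hours of the initial product infusion". A long list of known transplant complications follows, including fever, allergic reaction, pruritus and hypertension, and then: "For the purposes of this study, the listed events that are </= grade 3 will not be considered adverse events". Listed events of grade 4 or 5 go on the adverse event form. Acute GVHD, mixed chimerism and graft failure are set apart because they are collected as endpoints. Infusion reactions are not named there.

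**Two exceptions in X.8.** The first stands before the list. It covers known transplant complications or hematologic toxicities thought possibly attributable to the study. The second stands after the list. It covers known complications thought possibly attributable to the study procedure rather than to the transplant and its expected complications. Both say that such events are recorded and reported.

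**The concern.** The filters in X.8 are built to keep background transplant morbidity off the forms. The same section, however, explains its recording window by the primary aim, so in the visible text it is also where infusion reactions would be collected. Three endpoints are lifted out of the adverse event system by name, and the primary one is not.

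If site staff apply X.8 as written, a mild or moderate reaction reaches the form only through an attribution judgement, and the two exceptions word that judgement differently. The second is hard to apply here, because the study product is the transplant graft and allergic reaction is itself a listed complication. Losses can only lower the observed rate, which would then be set against a benchmark counted without a grade filter. What is at stake is the interpretation of the primary endpoint.

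**Working it through.** **1. Reproduce the benchmark (Section V).** Intervals are exact (Clopper-Pearson) 95%.
- Clinical infusions: 2/55 = 3.6% (0.4% to 12.5%).
- Study boosts: 0/22 = 0% (0% to 15.4%).
- Pooled: 2/(55 + 22) = 2/77 = 2.6% (0.3% to 9.1%). This mixes infusions with patients.

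The 2/55 and pooled point estimates both lie below 5%, so the plan's figure reproduces.

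**2. Put the two benchmark reactions through X.8.**
- Hypertension is on the list. At grade 3 or lower it is not an adverse event unless an exception applies.
- Urticaria is not named on the list. If it is classed as an allergic reaction, the listed-event filter and both exceptions apply. If not, the general grade 4+ rule applies, subject to how widely the first exception is read.

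Assume that both were grade 3 or lower (grades are not given) and that neither exception was used. The grade 4+ rule would then have turned 2/77 into 0/77 (0% to 4.7%).

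**3. Compare the two exceptions.**

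| | First (before the list) | Second (after the list) |
|---|---|---|
| Events covered | Known transplant complications or hematologic toxicities | The known complications just listed |
| Test | Possibly attributable to the study | Possibly attributable to the study procedure, and not to the transplant or expected complications |
| Case report form named? | No | No, although the grade 4-5 sentence beside it does name it |

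A febrile or allergic reaction during infusion could pass the first test and fail the second.

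**4. Expected counts in 80 patients (Sections IV.1a and VII.1).** Count = 80 × p.
- p = 2/77: 80 × 2/77 = 2.1
- p = 2/55: 80 × 2/55 = 2.9
- p = 5%: 80 × 0.05 = 4.0

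One reaction is 1/80 = 1.25 percentage points. Four reactions give 4/80 = 5.0% (1.4% to 12.3%). If two of the four went unrecorded, the report would show 2/80 = 2.5%.

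**5. Sensitivity to the share recorded.** Let s be the share of reactions that reach the form. This is an assumption, since the documents give nothing from which to estimate it. The chance of recording none is (1 − p·s)^80. With full capture (s = 1) it is 12% at p = 2/77, 5% at 2/55 and 2% at 5%. At p = 5%:

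| s | Expected recorded | Chance of recording none |
|---|---|---|
| 1 | 4.0 | 2% |
| 0.50 | 2.0 | 13% |
| 0.25 | 1.0 | 37% |
| 0.10 | 0.4 | 67% |

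A result of 0/80 has an upper 95% limit of 4.5%, so it would look consistent with a rate under 5% whatever the capture.

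**The case against.** The case for the plan is substantial.

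- **Section V already commits to recording reactions.** It is the specific statement for the primary endpoint, and X.8 is general reporting text, so a reader could let Section V govern. That is a fair reading. But X.8 itself invokes the primary aim and never points back to Section V.
- **The relevant text may be redacted.** The passages under Stem Cell Infusion, Safety of Product, Required Observations and Day of Graft Infusion are blacked out, and any of them could hold a capture rule. This stands: the documents do not show that capture is absent.
- **The exceptions have real reach.** The first extends to hematologic toxicities, precedes the list and follows a broad definition of expected events, so it is not clearly confined to listed terms. Both require the event to be recorded. This stands too. What remains is that the two tests differ and that neither names the form.
- **The damage is bounded.** The definition of a serious event in X.7 has no grade limit, serious events have their own reporting route, and attributable ones halt accrual pending review (Section VIII.1). The analysis is descriptive, with no test against 5%. A grade 4+ filter for background events is a deliberate choice that X.8 explains.

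A reader might go further and infer that urticaria has no route to being recorded, or that a finding of 0/80 is assured. The documents support neither. The first ignores the listed allergic reaction and the wider reading of the first exception. The second needs every reaction to be grade 3 or lower, and needs Section V and both exceptions to be disregarded.

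**Conclusion.** The inconsistency is in the visible text and is worth fixing. Section V sets no grade limit on the primary endpoint. X.8 applies two grade filters to the recording it links to that endpoint, and its exceptions do not agree with each other. The effect is confined to non-serious reactions of grade 3 or lower, and any bias favours the product.

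Its size is unknown. It depends on the grades of reactions, on how investigators apply the exceptions, and on whether Section V or redacted text already secures capture. With only about 2 to 4 reactions expected, missing even one or two would materially change the reported rate and its comparability with the ungraded benchmark. The conclusion is that reactions can be under-recorded, not that they will be. Patient protection against serious reactions is not in question. Confidence is medium, mainly because of the redactions.

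**What to change.** State in X.8 that the grade 4+ and listed-event filters do not apply to the Section V primary endpoint. For that endpoint, record on the case report form every infusion reaction that meets these conditions:
- any CTCAE v5.0 grade, listed or not;
- onset within the protocol's one-week adverse event window, counted from the infusion;
- judged at least possibly related to the infusion, whether or not the transplant could also explain it.

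Capture onset, grade and attribution. Use this one attribution test for infusion reactions in place of the two exceptions. If a redacted section already holds such a rule, cross-refer to it instead.

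Report the rate per patient for the initial infusion, with exact 95% intervals, and per infusion including any additional depleted products (allowed by Section IV.2c). Give both overall and by grade, and show onset within 48 hours separately. Section VI lists receipt of a second stem cell product as an off-study criterion, so the text should say that reactions to additional products are still collected. Note beside the results that the benchmark is ungraded and mixes patients and infusions. Keep the grade 4+ filter for all other adverse events.

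The cost is about 2 to 4 short form entries in 80 patients at the protocol's own rates, or more if conditioning effects are judged possibly related. The reported rate may also be less favourable. Relatedness remains an investigator's judgement, but recording it makes it visible.
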